Statistical Analysis Plan: In-Home Care for Patients with PSP and Related Disorders

NCT03552484

3-18-2019

Outcome ascertainment

Primary outcomes. The EQ5D will be completed at Visits 1-4 for program patients and annually for controls. This scale measures 5 domains of quality of life: *mobility, self care, usual activities, pain/discomfort, anxiety/depression*; each domain is scored from 1 to 5, with higher scores indicating better function. The scale also includes one item measuring overall self-rated health on a visual analogue scale (VAS) from 0 to 100, where 100 is “best health you can imagine”. This generic scale has been studied in PSP and related disorders and is available in an online format, supporting the feasibility of our control group. Change will be assessed in each EQ5D domain and in the VAS between baseline and 1 year. The instrument will also be administered at Visits 2 and 3 to avoid missing data if dyads are lost to follow-up prior to Visit 4. The MCSI will be completed at Visits 1-4 for caregivers, and annually for control caregivers. This scale is scored from 0-72, with 20-29 indicating moderate strain, 30 or higher indicating severe strain. MCSI scores will be evaluated as both continuous and categorical variables.

Demographics and confounders. include *race, ethnicity, education, insurance*, for patients and caregivers respectively; *living situation* (home or nursing facility), *diagnosis, diagnosis duration* (from year of onset or diagnosis, if onset unknown), and *comorbidities*.

Other variables of interest. The following items will be evaluated in program patients only: *hallucinations, motor severity (UPDRS, HY), and satisfaction* with the program (*Client Satisfaction Index-Short Form, CSI-SF*) administered to patients and caregivers.

Power calculation: Based on pilot recruitment, we anticipate enrolling 20 patients in home visits over 12 months, with a 15% drop out rate, yielding 17 patients at 12 months. We anticipate enrolling 100 control patients and 60 control caregivers, with a 20% drop out rate, yielding 80 patient and 48 caregiver controls. To detect a minimum clinically important difference of 6.5-8.0 in the EQ5D VAS, assuming a baseline mean of 37, standard deviation of 18, power of 0.80 and two-sided alpha of 0.05, we would require 42-63 patients.

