Data management: The primary data will be entered into a HIPAA-compliant database (**REDCap**), with quarterly audits for fidelity. Data will be exported to Stata 14 for analysis.

Data analysis:

Descriptive statistics. We will describe the demographics, disease characteristics, QoL, and caregiver strain at baseline in patients and caregivers. Categorical variables will be summarized by frequencies and percentages. Continuous variables will be assessed for normality and summarized by mean and standard deviation, or median and interquartile range. Adequacy of matching will be evaluated using chi-square and *t*-tests.

Bivariate analyses. Change in EQ5D subscores and VAS over 1 year will be compared between groups, stratified by diagnosis, by two-sample *t*-test or nonparametric Wilcoxon rank sum test. If a subject dies or is lost to follow-up, the last values of the EQ5D will be carried forward. We will analyze the association with change in EQ5D for each demographic, confounder, and covariate via chi square or multivariate ANOVA, as appropriate. We will compare change in MCSI over 1 year by group, stratified by diagnosis; if lost to follow-up, the last MCSI value will be carried forward.

Multivariable analyses. We will construct a linear regression model with change in EQ5D domains and VAS as sequential dependent variables, and treatment status as the primary independent variable, stratifying by diagnosis. We will build complex models to assess the contributions of each significant covariate. Model building will include manual stepwise, backward elimination checking for multicollinearity and confounding. We will construct similar models wherein MCSI change is the dependent variable.

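### The SAP stratifies the EQ5D and MCSI comparisons by diagnosis but names no diagnosis term or overall estimate, so the whole-group treatment effect is not secured

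*SAP*

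**What the plan says.** Under Bivariate analyses, the SAP states: "Change in EQ5D subscores and VAS over 1 year will be compared between groups, stratified by diagnosis". The tests named are a two-sample t-test or a Wilcoxon rank sum test. For caregivers: "We will compare change in MCSI over 1 year by group, stratified by diagnosis"; no test is named there.

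Under Multivariable analyses: "We will construct a linear regression model with change in EQ5D domains and VAS as sequential dependent variables", with "treatment status as the primary independent variable, stratifying by diagnosis". The MCSI models are to be similar. Covariates are then handled as follows: "Model building will include manual stepwise, backward elimination checking for multicollinearity and confounding".

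The SAP's list of confounders includes "diagnosis, diagnosis duration", so diagnosis is both a stratifier and a candidate covariate. The SAP does not list the strata. Protocol II.a names four diagnostic categories; the inclusion criteria in II.e name five, adding dementia with Lewy bodies. Protocol III.b mentions data analysis in its heading but covers only oversight and monitoring.

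Protocol I.a states its between-group hypotheses for home visit patients, and for their caregivers, as a whole.

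**The concern.** Neither a t-test nor a rank sum test has a place for a stratum. Without a stratified version of the test or a combining rule, stratifying by diagnosis naturally means repeating the test within each diagnosis. The regression sentence can be carried out the same way. An analyst who did so would follow the SAP and still produce no estimate of the effect that Protocol I.a asks about.

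The treated group is small, so splitting it is expensive. Each per-diagnosis interval would be too wide to tell an important benefit from an important harm on the SAP's own scale, and a diagnosis might have no treated patient at all. A second analyst, reading the same text as one diagnosis-adjusted model, would report a different quantity with an interval about half as wide.

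**Working it through.** **Inputs.** The SAP power calculation gives a minimum important VAS difference of 6.5 to 8.0 points, two-sided alpha 0.05, power 0.80, and an SD stated as "assuming a baseline mean of 37, standard deviation of 18". It expects 20 treated patients and 100 controls, falling to 17 and 80 at 12 months. Protocol II.a gives 25 and 60. The SAP also states: "If a subject dies or is lost to follow-up, the last values of the EQ5D will be carried forward". The number analysed may therefore be nearer 20 and 100 than 17 and 80, so all three pairs are shown.

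**Assumptions.** (a) SD 18 applies to change. The SAP gives it beside the baseline mean. With equal SDs at both times, SD of change = 18 × √(2(1 − r)), which equals 18 when the baseline-to-1-year correlation r is 0.50. (b) Diagnoses are equally common in both groups; the documents give no mix.

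**The plan's own figure.** The SAP's requirement of 42 to 63 patients reproduces exactly as a one-sample (paired) t-test with SD 18: n = 42 gives power 0.803 at 8.0 points, and n = 63 gives 0.806 at 6.5. It is neither a two-group nor a stratified calculation, so it does not show which reading was intended.

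**VAS precision and power.** SE = 18 × √(1/n₁ + 1/n₂); half-width = t(0.975, n₁ + n₂ − 2) × SE; power from the noncentral t distribution. Example, 17 and 80 pooled: SE = 18 × √(1/17 + 1/80) = 4.81, and half-width = 1.985 × 4.81 = 9.5. With four equal strata (4.25 and 20), SE = 9.61 and half-width = 2.073 × 9.61 = 19.9.

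| Treated / control | Analysis | Treated per analysis | 95% half-width | Power at 6.5 / 8.0 |
|---|---|---|---|---|
| 17 / 80 | pooled | 17 | 9.5 | 27% / 38% |
| 17 / 80 | 4 strata | 4.25 | 19.9 | 10% / 13% |
| 17 / 80 | 5 strata | 3.4 | 22.6 | 9% / 11% |
| 20 / 100 | pooled | 20 | 8.7 | 31% / 44% |
| 20 / 100 | 4 strata | 5 | 18.1 | 11% / 14% |
| 20 / 100 | 5 strata | 4 | 20.4 | 10% / 12% |
| 25 / 60 | pooled | 25 | 8.5 | 32% / 45% |
| 25 / 60 | 4 strata | 6.25 | 17.9 | 11% / 14% |
| 25 / 60 | 5 strata | 5 | 20.4 | 10% / 12% |

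Even the narrowest per-stratum half-width is 17.9 / 8.0 = 2.2 times the larger important difference. Adding diagnosis as a factor to the pooled model leaves power at 17 and 80 at 27% and 38%, if the diagnosis mix is the same in both groups.

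**Sensitivity to the SD.** At 17 and 80 and 8.0 points, SD 15 (r about 0.65) gives 51% pooled against 13 to 16% per stratum. SD 22 (r about 0.25) gives 27% against 9 to 10%. The contrast holds throughout.

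**MCSI.** No SD is given, so results are in SD units, assuming one caregiver per treated patient. The difference detectable with 80% power at 17 and 48 is 0.80 SD pooled, against 1.70 (four strata) or 1.94 (five). At 20 and 60 it is 0.73 against 1.53 or 1.74.

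**Empty strata.** The chance that at least one diagnosis has no treated patient, with 17 treated, is 3% for four equal strata and 11% for five. With 25 treated it is 0.3% and 2%. An assumed mix of 60/10/10/10/10 gives 54% and 27%, but that mix is purely illustrative.

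**The case against.** The strongest reply is that the regression sentence speaks of a single model with treatment as its main term, and that diagnosis is on the confounder list. One diagnosis-adjusted effect is then a fair reading, perhaps the more natural one for the regression, and a one-line clarification would settle it. This stands as far as it goes. A reader might infer that the SAP commits to separate analyses; it does not. But the adjusted reading fits the bivariate tests poorly, and nothing in the regression text secures it.

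A second reply is that Protocol II.a calls the study exploratory and that pooling does not reach 80% power. Both are true, and they lower the stakes. They do not supply the missing estimate.

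Two further inferences are not supported:

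- A reader might treat the unstated retention cutoff for backward elimination as a separate validity fault. The SAP names a confounding check, which largely guards against dropping real confounders, so an unstated cutoff alone is missing detail.
- A reader might count how many treatment effects each reading yields. No clean count exists, because the SAP analyses MCSI as both continuous and categorical and runs both bivariate and multivariable comparisons.

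**Conclusion.** The point holds as an ambiguity whose literal reading is costly. Taken literally, the SAP yields separate per-diagnosis analyses with about 3 to 6 treated patients each, and none gives the whole-group between-group effect in Protocol I.a. VAS half-widths would be 18 to 23 points with 9 to 14% power, against 8.5 to 9.5 points and 27 to 45% for one pooled analysis. These figures rest on SD 18 for change and equal strata, neither of which the documents state. An uneven mix would make the rarer diagnoses less precise still. Protocol I.a also hypothesises improvement within the home visit group; that is a different question and is not affected here. The change is worth making, at moderate priority given the exploratory status.

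**What to change.** In the SAP's analysis sections:

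- Make the primary between-group analysis of each EQ5D outcome, and of continuous MCSI, one pooled linear regression of change on treatment with diagnosis as a factor.
- Adjust for a short confounder list drawn from the SAP's own list, fixed before outcomes are seen and kept regardless of significance. Diagnosis duration, comorbidities and education would be one such list; the choice is the sponsor's.
- Report the treatment coefficient with its 95% CI. Show per-diagnosis results descriptively, without p-values.
- Keep backward elimination as a labelled sensitivity analysis.
- Report the estimate with and without adjustment for the baseline value of the outcome. The groups are not randomized, so the two can differ: with equal SDs the gap is (1 − r) × the baseline difference. For an assumed 10-point baseline difference that is 0.35 × 10 = 3.5 points at r = 0.65 and 0.75 × 10 = 7.5 at r = 0.25.
- Decide how sparse diagnoses will be grouped before outcomes are seen.

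The cost is SAP wording; the data and software are unchanged. Diagnosis-specific p-values are given up and a few degrees of freedom are spent. As a cautious bound, a simulation with nine covariate terms that explain nothing raised the SE at 17 and 80 by 5 to 14% (assumed imbalance 0 to 0.5 SD), taking power for 8.0 points from 38% to 30–35%; a shorter list should cost less. Homebound status, required only of the home visit arm, and motor severity, evaluated only in program patients, still cannot be adjusted for.
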